Cover Page

Title: Assessing and Promoting Resilience in Patients With Adult Congenital Heart Disease

NCT number: NCT04738474

Document date: Sept 5, 2025

Contents:

Study Protocol

Statistical Analysis Plan

(Research Coordinator's) Study Protocol <last updated 2023>

Specific Aim: Conduct a randomized pilot clinical trial to evaluate the feasibility and preliminary efficacy of the PRISM intervention among patients with ACHD.

Hypothesis: PRISM will be feasible and improve patient-reported resilience compared to usual care.

Description of PRISM sessions:

Topic	Skills	Format
1. Managing Stress	Mindfulness, Relaxation	One-on-One, In-Person or Video Chat
2. Setting Goals	Setting specific and realistic goals, planning for roadblocks	
3. Positive Reframing	Recognizing and replacing negative self-talk	
4. Making Meaning	Identifying benefits, gratitude, purpose, and legacy	
5. Advance Care Planning	Completion of sections of Voicing My Choices™ advance care planning tool for adolescents and young adults	
6. Coming Together	Discussion of what worked, plans for moving forward	Family Meeting
(i) Boosters/Worksheets	Between-session tools & practice	Individual

Questionnaire Elements:

- EuroQOL Scale (EQ5D-3L): 5-item tool used to assess quality of life (QOL) as it relates to health.
- Linear Analog Scale (LAS): Single item tool used to assess QOL on a continuous 0-100 scale.
- Hospital Anxiety and Depression Scale (HADS): 14-item tool to assess symptoms related to anxiety and depression. It is not intended to diagnose these conditions.
- Kessler-6 Psychological Distress Scale: 6-item inventory measuring the level of global psychological distress.
- Advance care planning (ACP) comfort: 2- question assessment of experience and comfort with ACP
- Connor-Davidson Resilience Scale (CD-RISC 10): 10-item measurement of inherent resiliency, created based on the original 25-item tool. Questions revolve around personal problem-solving and approaches to adversity.
- Perceived Competence Scale (PCS): 4-item tool that asks about one's competence in managing disease

Domain	Measurement Tool	Source & Collection Time
Patient-Centered Outcomes		
Quality of Life	EQ5D-3L & LAS (primary)	Patient; enrollment & 3 months
Psychological Distress	HADS; Kessler-6	Patient; enrollment & 3 months
Self-Efficacy (for health)	PCS	Patient; enrollment & 3 months
ACP Comfort	ACP assessment questions	Patient; enrollment & 3 months
Predictor: Resilience	CD-RISC 10 (primary)	Patient; enrollment & 3 months
Effect Modifier: Health Status	Independence in activities of daily living, presence of heart-related hospitalization in the last year, diagnosis of heart failure	Electronic health record, patient; enrollment

Potential Confounders: Demographics, Social Determinants of Health	Age, sex, race/ethnicity, marital status, education, family structure, residential information, heart lesion severity	Electronic health record, patient; enrollment
--	---	---

General Notes:

RC will keep complete and secure study records and adhere to protocol fidelity

RC will meet with PI **weekly, Thursdays 10am**, to discuss progress and any challenges; RC personal development goals will also be reviewed quarterly

RC will assist in the creation of a secure electronic database and maintain data using REDcap

Study Population:

Adult (18+ years) outpatients receiving care at the UW ACHD clinic

Patients with moderate or complex ACHD, stages C or D (stages A and B excluded; if needed, can expand back to stage B at a later date)

Must be able to participate in study activities independently and in English.

May not have another life-limiting illness or have participated in Aim 2. A life-limiting illness includes any illness known to be acutely terminal. Examples are cancer, Alzheimer's dementia, progressive neuromuscular diseases. RC will discuss with PI if uncertain.

If concern for cognitive impairment, patients will be screened with a six-item screening tool (Callahan 2002): 3-item recall [apple, table, penny], 3-item temporal orientation [day of the week, month, year].

Participant Enrollment:

RC will screen electronic patient lists for ACHD outpatient clinics to identify potential study participants.

RC will contact eligible patients (telephone and email), explain the study, and assess interest in participation using study team written and approved recruitment scripts.

If agreeable, patients will be enrolled into the study. RC will obtain informed consent.

Participants will be randomized to either the “intervention” (completion of PRISM) or “usual care” (non-directive, supportive care without PRISM) groups.

Randomization will occur following completion of baseline study measures and in a 1:1 ratio. The unit of randomization is the patient, and the randomization group will be the primary predictor of interest (PRISM or “usual care”). Group assignment will be determined using computerized random numbers with variable block sizes. Assignment will be provided to study staff in sealed, opaque, consecutively numbered envelopes (vs built into REDCap).

Participants and the RC will not be blinded; other staff will be blinded to the extent possible. Anticipated sample size of 60 total participants (30 per group). To achieve complete data for 60 participants, we anticipate enrolling 86 patients, 43 in each arm. Enrollment is anticipated within 9 months, may be extended 2-3 months if needed. Goal is to enroll at least 7 patients per month to reach the 1-year maximum.

Planned Enrollment Report

Racial Categories	Ethnic Categories				Total	
	Not Hispanic or Latino		Hispanic or Latino			
	Female	Male	Female	Male		

American Indian/Alaska Native	0	1	0	0	1
Asian	8	8	0	0	16
Native Hawaiian or Other Pacific Islander	1	0	0	0	1
Black or African American	2	2	1	1	6
White	24	24	3	3	54
More than One Race	3	4	0	1	8
Total	38	38	5	5	86

Study Measures and Data Collection:

RC will confirm and document contact information for study follow-up at enrollment.

RC will deliver the baseline questionnaire to all participants.

- Questionnaire will be completed either directly in REDCap via an emailed link, or on paper which will then be transcribed by study personnel into REDCap (if transcribed, will be double checked by another team member).
- At least 5 telephone and email attempts will be made to obtain responses, unless patients opt out
- RC will review responses within one week. If any responses suggest severe participant distress (HADS >16 (?) or K6 >12), RC will discuss with PI immediately.

RC will extract additional pertinent demographic information from medical records

- MRN
- Age
- Sex (Gender*)
- Race
- Ethnicity
- Insurance type
- ACHD diagnosis
- ACHD complexity (A&P classifications)
- Diagnosis of heart failure (or Fontan failure)
- Cardiac hospitalization in last year
- Diagnosis of mood or anxiety disorder (anxiety, depression, bipolar, post-traumatic stress disorder)

Usual Care group:

- No interim interventions apart from routine clinical care
- Direct any study questions to the PI
- At 3 months, RC will deliver the 3-mo questionnaire. At least 5 telephone and email attempts will be made to obtain responses, unless patients opt out.
- RC will provide gift cards (\$50) to participants ahead of final questionnaire completion.

Intervention group:

- Within 2 weeks of baseline data collection, RC will schedule an initial research visit to introduce PRISM and create a completion plan.
- Patients will subsequently schedule and participate in five 30-50-minute sessions (four core PRISM skills sessions and one ACP session), followed by one 30-50-minute "Coming Together" session with patients and their caregivers. ~~Ideally, the first session is conducted~~

~~in person~~ [changed Jan 2023] Sessions will occur using telephone or video chat. Each subsequent session will occur within 1-2 weeks of the previous session (=intervention completion by 3 months). At least 5 telephone and email attempts will be made to schedule sessions, unless patients opt out.

- After completing PRISM, RC will deliver the 3-mo questionnaire. At least 5 telephone and email attempts will be made to obtain responses, unless patients opt out.
- RC will provide gift cards (\$50) to participants ahead of final questionnaire completion. Study-related activities (such as parking; case-by-case basis, discuss with PI) will also be reimbursed.
- RC will conduct “exit interviews” with a subset of PRISM participants (discuss with PI) to gather feedback about the experience/intervention. A modest gift card will be provided to interview participants.
- RC will keep notes on patient interactions and any feedback or comments provided during or related to sessions. This will occur in a separate “PRISM Memos/Feedback” document.

Statistical Analysis Plan

(As Published in *Contemporary Clinical Trials*, October 2024;
<https://doi.org/10.1016/j.cct.2024.107638>)

Our primary aim is to describe feasibility, defined by the proportion of patients who a) enroll in the study among those who are eligible during the recruitment period, and b) complete the PRISM intervention among those randomized to that arm. We anticipate 70% enrollment and retention rates. We will also gain insight into feasibility from a qualitative content analysis of transcribed exit interview data. We anticipate that transcriptions will be reviewed by two study team members, using an inductively developed coding matrix to identify and organize topics discussed. Finally, the research coordinator and PRISM coach will provide an assessment of feasibility from the interventionist standpoint, summarizing study conduct adaptations and barriers that must be addressed in future studies, or if PRISM were to be implemented at scale in the ACHD population.

Additionally, we will evaluate the efficacy of the PRISM intervention to increase resilience in this population. We will evaluate the difference in mean resilience at 3 months after randomization between participants randomized to PRISM and participants randomized to usual care, following the intent-to-treat principle. We will adjust for resilience score at randomization, via a linear regression model, as resilience at randomization and 3 months later (after the intervention period) will likely be highly correlated and thus the adjustment will improve our precision. In exploratory analyses, we will evaluate the effect of the PRISM intervention on QOL, psychological distress, perceived competence for health care management, and comfort with advance care planning using analogous analyses.

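### Do the exploratory outcomes need a named lead scale and score in the SAP before the analysis is sound?

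*Combined protocol and SAP*

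**What the plan says.** The Statistical Analysis Plan makes feasibility the primary aim. It then compares mean 3-month resilience between arms by linear regression adjusted for the baseline score. One closing sentence covers four exploratory constructs (quality of life, psychological distress, perceived competence, comfort with advance care planning) and applies the same type of model. It names no questionnaire, total or subscale for any of them.

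The instruments are in the protocol, under Questionnaire Elements and in the measures table that follows:

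- **Quality of life:** "EQ5D-3L & LAS (primary". The EQ5D-3L is a "5-item tool used to assess quality of life (QOL) as it relates to health"; the LAS is a "Single item tool used to assess QOL on a continuous 0-100 scale".
- **Distress:** "HADS; Kessler-6". HADS is a "14-item tool to assess symptoms related to anxiety and depression".
- **Self-efficacy:** the four-item PCS alone.
- **Advance care planning:** a "2- question assessment of experience and comfort with ACP".
- **Resilience:** the row is labelled "Predictor: Resilience" and its tool is given as "CD-RISC 10 (primary".

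The table places all of these at enrollment and 3 months.

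**The concern.** The regression that the SAP carries over needs one numeric score per outcome, and the SAP supplies none for the exploratory set. The protocol offers two scales each for quality of life and distress. It does not say how five EQ5D-3L items become one number, whether the HADS anxiety and depression items are combined, or how the advance care planning questions are scored. The primary tag on the quality-of-life row is unexplained, and the distress row has none.

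An analyst who wanted a favourable result could therefore decide afterwards which scale represents a construct. With about 30 complete participants per arm, choosing the better of two noisy estimates would create some apparent benefit from nothing. Because the Specific Aim includes preliminary efficacy, such an estimate could influence outcome choice in a later trial.

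The predictor label on the resilience row adds to the impression that the table was not written with the analysis in mind.

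**Working it through.** **1. The plan's own sample-size figure.** Participant Enrollment wants 60 participants with complete data, and the SAP expects 70% retention. 60 / 0.70 = 85.7, rounded up to 86, or 43 per arm. This matches the stated enrollment, so 30 per arm is the right basis for what follows.

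**2. What is really open.** Setting the SAP sentence beside the measures table:

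| Construct in SAP | Tools in protocol | Open point |
|---|---|---|
| Quality of life | EQ5D-3L, LAS | two scales; EQ5D-3L scoring |
| Distress | HADS, Kessler-6 | two scales; HADS total or parts |
| Perceived competence | PCS | none on choice of scale |
| Advance care planning comfort | two questions | scoring |

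That is 2 + 2 + 1 + 1 = 6 instruments for four constructs. The choice of scale is open in two constructs, giving 2 × 2 = 4 possible one-scale-per-construct sets. The two advance care planning questions are not clear rivals: together they cover experience and comfort, and the SAP asks only about comfort.

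**3. The tag.** On the resilience row the tag directly follows the single tool that it marks. Read the same way on the quality-of-life row, it marks the LAS, the tool that it follows. This is the most natural reading, though not the only one.

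**4. The predictor label.** Participant Enrollment makes randomized group the predictor of interest, and the SAP makes 3-month resilience the outcome with its baseline value as covariate. The model is unambiguous, so the label is a clerical slip.

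**5. The worst case, if one scale were picked after the fact.** The documents give no significance level and no correlations. Assumptions: two-sided 5% (critical value 1.96), correlation r between the two adjusted estimates of 0.3 to 0.8, baseline-to-3-month correlation 0.5, 30 per arm, no true effect, and both scales oriented so that higher is better.

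- Standard error of the adjusted difference: √(2/30) × √(1 − 0.5²) = 0.258 × 0.866 = 0.224 SD. The 95% half-width is 1.96 × 0.224 = 0.44 SD.
- Chance of a nominally significant benefit on at least one scale: 1 − P(Z₁ ≤ 1.96 and Z₂ ≤ 1.96), bivariate normal.
- Chance of a significant result in either direction: 1 − P(|Z₁| ≤ 1.96 and |Z₂| ≤ 1.96).
- Expected value of the larger estimate: SE × √((1 − r)/π).

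| r | Benefit on at least one | Either direction | Expected spurious gain |
|---|---|---|---|
| 0.3 | 4.8% | 9.5% | 0.224 × 0.472 = 0.106 SD |
| 0.5 | 4.5% | 9.1% | 0.224 × 0.399 = 0.089 SD |
| 0.8 | 3.9% | 7.8% | 0.224 × 0.252 = 0.056 SD |
| one scale only | 2.5% | 5.0% | 0 |

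The benefit column is the relevant one, because the either-direction column also counts apparent harm. Varying the baseline correlation from 0.3 to 0.7 widens the expected gain to 0.047–0.116 SD. At a baseline correlation of 0.5, the gain is a quarter to just under a half of one standard error (0.056/0.224 = 0.25; 0.106/0.224 = 0.47).

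**6. If both scales are reported,** nothing is selected, and this bias does not arise.

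**The case for a change.** The best case for a change is that it costs almost nothing. One line per construct, naming the scale and its score, would remove the freedom to choose and need no new data. The exploratory label does not tell a reader which scale was intended, and the table lists the tools without ranking or scoring them. For distress in particular, no reading of the table yields a lead.

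The textual part of this stands: the SAP sentence is silent on instruments, no lead distress scale is given, and scoring is not described. What does not follow is that the results are at risk. The SAP does not name the CD-RISC 10 for resilience either, and nobody would doubt which scale is meant, because the protocol supplies it. The exploratory scales are supplied in the same way. The SAP text is also marked as reproduced from a journal article, so its silence is weak evidence that scoring was never settled.

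The harm further depends on picking one scale per construct, which the plan nowhere describes. Where two tools are listed and collected at both times, the ordinary course is to analyse both.

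Timing weakens the benefit as well. The SAP text dates from October 2024 and the document from September 2025. If 3-month data have already been seen by arm, naming a lead now would not be pre-specification, and the sensible course would again be to report both.

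The query mark beside the HADS threshold in Study Measures and Data Collection concerns when the coordinator alerts the investigator. It does not define an outcome score.

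**Conclusion.** This is missing detail that an analyst would fill sensibly, together with one clerical label. It does not call for a change. The protocol connects every exploratory construct to its instruments and time points. Estimating each listed scale with its confidence interval, labelled exploratory, is consistent with the text and free of selection. An author revising the document for other reasons could usefully state the scores used and explain or drop the primary tag, but that is a matter of clarity.

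Even under the unfavourable assumption of best-of-two selection, the chance of a false nominal benefit per two-scale construct rises from 2.5% to between 3.9% and 4.8%. The expected inflation of 0.06 to 0.11 SD is small beside an interval of ±0.44 SD. The percentages rest on an assumed two-sided 5% level and between-scale correlation of 0.3 to 0.8. The SD figures also assume a baseline correlation of 0.5 and 30 per arm. Neither the feasibility aim nor the resilience comparison depends on any of this.

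### Do the effect-modifier, confounder and predictor labels in the measures table require analyses that the SAP leaves out?

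*Combined protocol and SAP*

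**What the plan says.** The measures table near the start of the Study Protocol gives variables analytic roles. One row is headed "Effect Modifier: Health Status" and lists "Independence in activities of daily living, presence of heart-related hospitalization in the last year, diagnosis of heart failure". The next, "Potential Confounders: Demographics, Social Determinants of Health", lists eight items if race and ethnicity count as one. Both rows give the chart and the patient as sources, at enrolment. Resilience (CD-RISC 10, at enrolment and 3 months) is labelled a predictor and tagged as primary. The QOL row begins "EQ5D-3L & LAS (primary", with the tag directly after LAS. The distress row names HADS and Kessler-6 without a tag.

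Study Measures and Data Collection adds a chart list, introduced by "RC will extract additional pertinent demographic information from medical records". Participant Enrollment states that the randomised arm is the main predictor.

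The SAP begins "Our primary aim is to describe feasibility". Its efficacy analysis is the between-arm difference in mean 3-month resilience by intention to treat, and it says "We will adjust for resilience score at randomization, via a linear regression model". It continues "In exploratory analyses, we will evaluate the effect of the PRISM intervention on QOL, psychological distress", and covers perceived competence and comfort with advance care planning in the same way. It has no interaction, no subgroup analysis and no demographic covariate.

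**The concern.** Effect modifier and confounder are analytic roles, so a reader expects the SAP to contain an interaction and an adjusted model. It contains neither. A later finding that PRISM works differently by health status could then be called planned, because the protocol names the modifier, or post hoc, because the SAP does not. One of the three variables defining health status, independence in daily living, is in neither the questionnaire list nor the chart list, which raises the question of whether it was collected.

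Two labels add to the doubt. Resilience is called a predictor although it is the efficacy outcome. The primary tag sits on QOL although the SAP makes QOL exploratory. The SAP names constructs and no instruments, and QOL and distress have two instruments each, so the score to be reported looks open to choice. What is at stake is the standing of any health-status result and possible selective reporting of two exploratory outcomes.

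**Working it through.** **Sample size.** The protocol wants complete data on 60 participants, 30 per arm, and the SAP expects 70% retention. 60 / 0.70 = 85.7, rounded up to 86, and 30 / 0.70 = 42.9, rounded up to 43 per arm. Both match the protocol, so 30 completers per arm is the right basis for what follows.

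**Coverage of the variables.** I matched each item in the two rows to the Questionnaire Elements and the chart list.

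| Role in table | Items | In a list | Not in a list |
|---|---|---|---|
| Effect modifier | 3 | 2 (hospitalisation, heart failure) | 1 (daily-living independence) |
| Potential confounder | 8 | 4 (age, sex, race/ethnicity, lesion severity) | 4 (education, marital status, residence, family structure) |
| Total | 11 | 6 | 5 |

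The five unlisted items are still in the measures table, whose last column gives source and timing. The Questionnaire Elements describe the scored instruments, the chart list is introduced as additional, and neither is said to be exhaustive. The baseline form is not in the documents. The lists therefore do not show that these items go uncollected.

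**Which text defines the analysis.** The protocol is marked as last updated in 2023, and the SAP is given as published in October 2024. The later text specifies the models, while the table rows specify none. A modifier analysis would therefore be post hoc.

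**Predictor and outcome.** Participant Enrollment makes the arm the predictor. The SAP makes 3-month resilience the outcome and baseline resilience a covariate. The hypothesis also has PRISM improving resilience. Only the table label disagrees, and no model follows from it.

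**Confounders.** Allocation is random, so leaving out demographic covariates does not bias the intention-to-treat contrast. The plan expects 86 − 60 = 26 participants without complete data. Selective loss among them would be a missing-data question, which the confounder row neither creates nor settles.

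**What an interaction would deliver.** Work in SD units with 30 per arm. The documents give no health-status split and no baseline correlation, so both are assumed.

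- Overall effect: SE = √(1/30 + 1/30) = 0.258; half-width = 2.002 × 0.258 = 0.517.
- Interaction, 50/50 split (15 per cell): SE = √(4/15) = 0.516; half-width = 2.003 × 0.516 = 1.034. The SE is 2.0 times that of the overall effect.
- Interaction, 20/80 split (6 and 24 per cell in each arm): SE = √(2/6 + 2/24) = 0.645; half-width = 1.293. The SE ratio is 2.5.
- With a baseline correlation of 0.7, multiply by √(1 − 0.49) = 0.714. The half-widths become 0.369 overall, and 0.739 and 0.924 for the interaction.

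**Instruments.** The four exploratory constructs map to six measures: EQ5D-3L, LAS, HADS, Kessler-6, PCS and the advance-care-planning questions. If one score each were picked for QOL and distress, there would be 2 × 2 = 4 possible pairs. Nothing in the SAP restricts reporting to one per construct, and the table names both in each case.

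**The case for a change.** The best case for a change is that the protocol chose words with analytic meaning. Naming an effect modifier in advance gives a later subgroup claim some cover, and one sentence in the SAP would remove it. The chart list is specific enough to include insurance type and mood diagnoses, so the absence of daily-living independence and four social items looks more like an oversight than shorthand. The SAP names no instrument, so the table is the only link from construct to score, and its one tag on QOL can be read as covering LAS alone or both tools. Pilot results may inform later studies, which the SAP itself mentions.

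Part of this stands. The labels do not fit the SAP, the tag is undefined, and distress has no lead score. The rest does not carry. A row label with no model, coding or contrast does not pre-specify an analysis, so it gives little cover. The omission from two lists is outweighed by the table's own statement of source and timing. The instrument choice matters only if an analyst suppresses one of two measures that the protocol commits to collecting, and both constructs are openly exploratory.

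**Conclusion.** No change follows. The mismatch consists of three unused or misplaced role labels, one undefined tag, and five of eleven items that are in the table but not in the other lists. Followed as written, the plan still gives a sound description of feasibility and a sound randomised comparison of 3-month resilience. Analysts would ordinarily report the health-status and demographic variables as baseline descriptors by arm, present both QOL and both distress instruments, and call any health-status contrast post hoc.

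A formal interaction would have a half-width of 0.74 to 1.29 SD, against 0.37 to 0.52 SD for the overall effect. That range rests on a binary health-status variable, splits of 50/50 to 20/80 and a baseline correlation of 0 or 0.7, none of which the documents give. The figures describe an analysis that no document plans, and they support leaving it out.

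The conclusion assumes that the SAP defines the analyses and that the measures table describes what is collected. A report that presented a health-status interaction as planned, or only one of two collected instruments, would deserve criticism, but the fault would lie in the reporting.

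### Does a recruitment goal of at least 7 patients a month contradict the plan to enrol 86?

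*Combined protocol and SAP*

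**What the plan says.** All the recruitment figures stand together in the Study Protocol, in the text on randomization and sample size under Participant Enrollment. On the total: "To achieve complete data for 60 participants, we anticipate enrolling 86 patients, 43 in each arm". On the calendar: "Enrollment is anticipated within 9 months, may be extended 2-3 months if needed". The monthly pace comes next: "Goal is to enroll at least 7 patients per month to reach the 1-year maximum". The Planned Enrollment Report that follows also totals 86.

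The Statistical Analysis Plan supplies the rate that links 60 to 86: "We anticipate 70% enrollment and retention rates". Its primary aim is to describe feasibility. The comparison of resilience at 3 months is an additional analysis, and no power, effect size or threshold for success is given.

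Two other parts of the protocol bear on how accrual is watched. General Notes has the research coordinator meet the principal investigator every week about progress and difficulties. Study Population allows eligibility to be widened to stage B if that proves necessary.

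**The concern.** Three consecutive sentences give a total, a period and a pace, and a reader naturally multiplies the last two. Seven a month over the expected 9 months is 63, which is 23 short of 86. The pace is also too low for an 11-month period and, strictly, for 12 months. The extension is presented as a contingency, yet the only monthly figure in the protocol uses all of it from the start.

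If the pace were the working yardstick, a coordinator exactly on goal could seem to be on schedule while falling well behind the 9-month plan. The trial might then end with fewer than 60 complete records. In a pilot whose primary aim is feasibility, with enrolment as one of its two measures, an inconsistent accrual plan would deserve attention.

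**Working it through.** **Inputs.** From Participant Enrollment: 60 with complete data (30 per group), 86 enrolled (43 per arm), 9 months extendable to 11 or 12, and at least 7 per month. From the Statistical Analysis Plan: 70% retention. I assume that this rate applies to complete 3-month data in both arms.

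**The plan's own total.** 60 / 0.70 = 85.7, rounded up to 86. Per arm, 30 / 0.70 = 42.9, rounded up to 43. Both stated figures reproduce exactly, which supports the assumption about retention.

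**Pace needed and pace stated.** Rate needed = 86 / months. Enrolled at the floor = 7 × months. Expected completers = enrolled × 0.70.

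| Months | Rate needed for 86 | Enrolled at exactly 7 | Short of 86 | Expected completers |
|---|---|---|---|---|
| 9 | 9.56 | 63 | 23 (27%) | 44.1 |
| 11 | 7.82 | 77 | 9 (10%) | 53.9 |
| 12 | 7.17 | 84 | 2 (2.3%) | 58.8 |

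At exactly 7 a month, 86 is reached after 86 / 7 = 12.3 months.

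**Which row applies.** The sentence names the 1-year maximum, so the 12-month row is the relevant one. There, 7 is 7.17 rounded to a whole patient.

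**Effect of the floor wording.** Ten months at 7 and two months at 8 give 70 + 16 = 86. That sequence meets the goal in every month and reaches the full target within the year.

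**What the 2 patients are worth.** With independent retention at 70%, the binomial chance of at least 60 completers is 0.44 with 84 enrolled and 0.57 with 86. Even the full target is only a little better than an even chance. With 84 enrolled, retention of 60 / 84 = 71.4% yields 60 completers, so 1.4 percentage points on an anticipated rate close the gap.

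**The case for a change.** The best argument for a change is that the protocol gives no pace for the period it actually expects. Nine months needs about 9.6 patients a month, which at 70% enrolment means 9.56 / 0.70 = 13.7 eligible patients a month. The stated floor implies 7 / 0.70 = 10. Those are different screening loads for one coordinator at one clinic. If the extension were only 2 months, as the text allows, exactly 7 a month would give 77 enrolled and about an 8% chance of 60 completers. A floor below the planned pace might also delay the decision to widen eligibility.

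The arithmetic stands, and so does the observation that no 9-month pace is stated. The harm does not follow. The coordinator has the total of 86 and the 9-month expectation in the same place as the monthly goal. Weekly meetings with the principal investigator would show 63 of 86 at month 9, when the extension is decided, and a slow pace could be seen well before then. Nothing in the documents makes the monthly figure the sole measure of accrual. An expected duration given alongside a minimum pace for the outer limit is ordinary planning.

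**Conclusion.** The concern does not call for a change. Read as written, the goal is a floor for a 12-month limit. At exactly that floor it falls 2 patients (2.3%) short of 86, or 60 − 58.8 = 1.2 expected completers short of 60, because 7.17 was rounded down. It is not true that meeting the goal means missing 60: a coordinator can meet it and enrol 86. The gap of 23 patients comes from setting a 12-month minimum against a 9-month forecast.

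A rewording would bring no gain. The trial is a pilot that describes feasibility, and no stated power, threshold or decision depends on the monthly pace or on reaching 60. Giving about 10 a month for 9 months, or 8 as the whole-patient minimum for 11 to 12 months, would be a little tidier but would alter no analysis. Extending the timeline to 12 to 13 months would exceed the protocol's own 1-year maximum to recover 2 patients.

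This rests on reading the goal as tied to the 1-year maximum, which is what the sentence says, and on 70% retention in both arms, which reproduces the 86.
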